6.5 Adjustment for Covariates

Statistical analyses for efficacy endpoints including ANCOVA model with covariates are detailed in Sections 6.3.4 and 6.3.5 of this document.

6.6 Handling of Dropouts and Missing Data

For patients who do not have the baseline values or patients who drop out prematurely and/or do not have a valid measurement in mean daily non-sedentary daytime activity between weeks 10-12, a Multiple Imputation (MI) method will be used for the primary analysis. For the key secondary variable the same imputation strategy will be used.

Multiple imputation (MI)

The MI procedure in the SAS Software is a multiple imputation procedure that creates multiply imputed data sets for incomplete p-dimensional multivariate data. It uses methods that incorporate appropriate variability across the m imputations. Once the m complete data sets are analyzed by using standard procedures, the MIANALYZE procedure can be used to generate valid statistical inferences about these parameters by combining results from the m complete data sets:

- The missing data are filled in m times to generate m complete data sets.
- The m complete data sets are analyzed by using standard procedures.
- The results from the m complete data sets are combined for the inference.

The MI process through SAS software:

1. To explore missing data patterns

```
PROC MI DATA=example NIMPUTE=0;  
  VAR [list of variables];  
  RUN;
```

2. To select the most appropriate MI method (see appendix 8.5)
3. Process of imputation with PROC MI. Imputation step
4. SAS statistical procedure to analyze each MI repetition (MIXED,MEANS, GENMOD...). Analysis step
5. Finally, the MIANALYZE procedure combines the results and provides valid statistical inferences. Pooled step.

Sensitivity analysis LOCF. For patients who drop out prematurely and/or do not have a valid measurement in mean daily non-sedentary daytime activity between weeks 10-12, the last

available value of non- sedentary daytime activity over two weeks under treatment will be used for the primary analysis (last-observation-carried-forward principle, LOCF). Patients with major protocol violations, but with a valid assessment of the primary variable will be included in the primary analysis with their observed value. For the key secondary variable the same imputation strategy will be used.

For the analyses of further secondary and of the exploratory endpoints referring to data at 'end of study' the same algorithm will be applied to create an extra LOCF visit next to the usual Week 12 visit. This additional 'end of study' measure constitutes a conservative approach in handling of missing data and ensures much as possible unbiased and comparable efficacy results.

In case of qualitative (e.g., increased level of non-sedentary daytime physical activity) or semi-quantitative (e.g., PGA) efficacy variables, missing Week 12 values of patients previously dropped out due to hospitalization or death will be substituted by the worst value possible for the respective variable (e.g., increased level of non-sedentary daytime physical activity="No", PGA="much worse").

In the event that any date for Adverse Events is incomplete after Data Management processing and this date needs to be used for a calculation, the following will be assigned for the missing date:

- if no field is available: no imputation will be performed
- if only the year is available:
 - Onset date: day "01" and month of "January" or first dose administration date, whatever occurs after will be imputed
 - End date: day "31" and month of "December" or EOS date, whatever occurs before will be imputed
- if the month and year are available:
 - Onset date: day "01" will be imputed
 - End date: "last day of the month" will be imputed

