9.4.2 Statistical model, hypothesis, and method of analysis

6-minute walk test: The primary hypothesis to be rejected is that the change in 6-minute walk test between baseline and 'end of study' under sacubitril/valsartan is equal to the change under enalapril.

Non-sedentary daytime activity: The primary hypothesis to be rejected is that the change in weighted mean non-sedentary daytime activity between baseline and 'end of study' under sacubitril/valsartan is equal to the change under enalapril. Both analyses will be performed in the same way, let μ_j denote the expected change in 6-minute walk test or mean daily non-sedentary daytime activity in group j , $j=0,1$ where

- 0 corresponds to treatment with sacubitril/valsartan and
- 1 corresponds to treatment with enalapril.

The following hypothesis will be tested:

$$H_0: \mu_0 = \mu_1 \text{ vs. } H_1: \mu_0 \neq \mu_1$$

The primary efficacy variable will be analyzed using analysis of covariance (ANCOVA), with factors treatment and baseline NYHA class (NYHA II vs. III/IV) and the baseline value as covariates. The two-sided 95%-confidence interval and the corresponding p-value for the between-group difference of the adjusted means (least square means) of both treatment groups will be provided from the ANCOVA model.

Confirmatory testing, i.e. the primary analysis of the primary variable, will be carried out for the FAS. The level of significance will be set to $\alpha = 0.05$ (two-sided).

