9.4.3 Handling of missing values/censoring/discontinuations

For patients who do not have the baseline values or patients who drop out prematurely and/or do not have a valid measurement in mean daily non-sedentary daytime activity between weeks 10-12, a Multiple Imputation (MI) method will be used for the primary analysis.

In case of qualitative (e.g., increased level of non-sedentary daytime physical activity) or semi-quantitative (e.g., PGA) efficacy variables, missing Week 12 values of patients previously dropped out due to hospitalization or death will be substituted by the worst value possible for the respective variable (e.g., increased level of non-sedentary daytime physical activity="No", PGA="much worse").

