6.3.5 Primary Efficacy analysis

One of the primary end-points is the change from baseline to 'end of study' in the 6-minute walking test.

The aim of the primary analysis of this study is to assess differences between sacubitril/valsartan and enalapril patients with respect to the primary endpoint in the FAS population excluding the patients who have an AE/SAE (non-HF related) during/around the 6-minute walking test which directly is causally linked to the 6-minute walking test performance.

Change from baseline values will be summarized. The comparison of treatment groups will be carried out using an ANCOVA model adjusting for treatment and baseline NYHA class (NYHA II vs. III/IV) and the baseline value as covariates.

The following hypothesis will be tested:

$H_0: \mu_0 = \mu_1$ vs. $H_1: \mu_0 \neq \mu_1$

Where 0 corresponds to treatment with sacubitril/valsartan and 1 corresponds to treatment with enalapril.

$6MWT_0$ = 6-minute walking test at baseline (week 0).

$6MWT_1$ = 6-minute walking test EOS (week 12).

$6MWT_{ch}$ = change in 6-minute walking test from baseline ($6MWT_1 - 6MWT_0$).

$GROUP_k$ = treatment group.

$NYHA_{0i}$ = baseline NYHA class

ANCOVA model:

$6MWT_{chi} = \mu + GROUP_k + 6MWT_{0i} + NYHA_{0i} + e_{ik}$

where:

$6MWT_{chi}$: change in 6-minute walking test for each subject i.

μ : global mean

$GROUP_k$: treatment group

$6MWT_{0i}$ = 6-minute walking test baseline (week 0) value for each subject i.

$NYHA_{0i}$ = NYHA class baseline value for each subject i.

e_{ik} : associated unobserved error term.

Other primary endpoint is the change from baseline to 'end of study' in mean daily non-sedentary daytime activity (defined as ≥ 178.50 activity counts per minute) as calculated by the MotionWatch 8 accelerometer device. Baseline is defined as the average minutes per day in non-sedentary daytime activity over 2 weeks (week -2 to week 0) prior to randomization and 'end of study' is defined as the average minutes per day in non-sedentary daytime activity between week 10 to week 12.

The aim of the primary analysis of this study is to assess differences between sacubitril/valsartan and enalapril patients with respect to the primary endpoint in the FAS with MI.

Change from baseline values will be summarized. The comparison of treatment groups will be carried out using an ANCOVA model adjusting for treatment and baseline NYHA class (NYHA II vs. III/IV) and the baseline value as covariates.

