6.3.7 Sensitivity analyses

6-minute walking test:

For the main analysis the patients who have an AE/SAE (non-HF related) during/around the 6-minute walking test which directly is causally linked to the 6-minute walking test performance will be removed. A sensitivity analysis will be performed including all patients for each population.

Main analysis for 6-minute walking test primary variable:

FAS population subset patients without AE/SAE (non-HF related) during/around the test

Sensitivity analyses for 6-minute walking test primary variable:

FAS population

PP population

PP population subset patients without AE/SAE (non-HF related) during/around the test

Mean daily non-sedentary daytime activity:

In addition to the primary analysis, the primary efficacy variables will also be analyzed using the same analysis model in the PP population as supportive. Furthermore, the analysis of the

primary variable (mean daily non-sedentary daytime activity) will be repeated in the FAS population without MI of missing values.

Besides, the last-observation-carried-forward principle (LOCF) imputation method will be performed as a sensitivity analysis (Section 6.6).

Main analysis for mean daily non-sedentary daytime activity primary variable:

FAS population with MI

Sensitivity analyses for mean daily non-sedentary daytime activity primary variable:

PP population with MI

PP population with LOCF

PP population without MI

FAS population without MI/LOCF

FAS population with LOCF

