14.2 EFFICACY DATA

Primary efficacy analysis

Table 14.2-1 6-minute walking test: absolute and change between baseline and end of study by treatment group.
FAS population/PP population/FAS population subset patients without AE/SAE/PP population subset patients without AE/SAE
Descriptive statistics

Table 14.2-2 6-minute walking test: ANCOVA comparison of change between baseline and end of study.
FAS population/PP population/FAS population subset patients without AE/SAE/PP population subset patients without AE/SAE
Statistical (mixed model) by treatment group

Table 14.2-3 Mean daily non-sedentary daytime activity: absolute and change between baseline and end of study by treatment group.
FAS population with MI/FAS population with LOCF/FAS population without MI/LOCF/PP population with MI/ PP population with LOCF/PP population without MI
Descriptive statistics

Table 14.2-4 Mean daily non-sedentary daytime activity: ANCOVA comparison of change between baseline and end of study.
FAS population with MI/FAS population with LOCF/FAS population without MI/LOCF/PP population with MI/ PP population with LOCF/PP population without MI
Statistical (mixed model) by treatment group

Secondary efficacy analysis

Table 14.2-5 Improved performance (≥ 30 m) in 6MWT: proportion of patients at the end of study by treatment group.
FAS population/FAS population subset patients without AE/SAE
Descriptive statistics

Table 14.2-6 Improved performance (≥ 30 m) in 6MWT: logistic regression model.
FAS population/FAS population subset patients without AE/SAE
Statistical (logistic model) by treatment group

Table 14.2-7 Improved performance (≥ 30 m) in 6MWT for patients with baseline 6MWT equal to or less than 300 meters: proportion of patients at the end of study by treatment group.
FAS population/FAS population subset patients without AE/SAE
Descriptive statistics

Table 14.2-8 Improved performance (≥ 30 m) in 6MWT for patients with baseline 6MWT equal to or less than 300 meters: logistic regression model.
FAS population/FAS population subset patients without AE/SAE
Statistical (logistic model) by treatment group

Table 14.2-9 Improved performance (≥ 30 m) in 6MWT for patients with baseline 6MWT between 100-450 meters: proportion of patients at the end of study by treatment group.
FAS population/FAS population subset patients without AE/SAE
Descriptive statistics

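### Imputation is specified for the activity co-primary only; the 6MWT co-primary as listed drops every patient without both walks and has no missing-data sensitivity analysis

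*SAP*

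**What the plan says.** **Activity co-primary.** SAP 6.3.5 assesses the treatment difference "with respect to the primary endpoint in the FAS with MI". SAP 6.3.7 adds five sensitivity analyses, which together with the main one cross FAS and PP with MI, LOCF and no imputation. Tables 14.2-3 and 14.2-4 carry the same list, beginning "FAS population with MI/FAS population with LOCF/FAS population without MI/LOCF/PP population with MI".

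**6MWT co-primary.** SAP 6.3.5 models one value per patient, week-12 distance minus week-0 distance, on treatment, baseline distance and NYHA class. It names no missing-data method. SAP 6.3.7 gives the main analysis as "FAS population subset patients without AE/SAE (non-HF related) during/around the test", with the full FAS, the PP set and the matching PP subset as sensitivity analyses. Tables 14.2-1 and 14.2-2 list "FAS population/PP population/FAS population subset patients without AE/SAE/PP population subset patients without AE/SAE" and nothing on imputation.

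**Who is in the FAS.** SAP 5 asks for a baseline value and any post-baseline value on at least one of the two primary endpoints.

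**Wording that reaches further.** Protocol 9.4.2 says of the two co-primaries: "Both analyses will be performed in the same way". The MI rule in Protocol 9.4.3, repeated in SAP 6.6, opens "For patients who do not have the baseline values or patients who drop out prematurely and/or do not have a valid measurement". Only the last of those three conditions is tied to activity: in SAP 6.6, for patients who "do not have a valid measurement in mean daily non-sedentary daytime activity between weeks 10-12, a Multiple Imputation (MI) method will be used". Protocol 9.4.4 limits LOCF to activity.

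**The concern.** The 6MWT was raised to co-primary in Amendment 4 because the sponsor had come to doubt accelerometry. Yet the endpoint the sponsor now trusts more has the weaker missing-data plan. A change score with no imputation silently removes any FAS member who lacks either walk. That includes patients who entered the FAS through actigraphy alone, or through a week-4 or week-8 walk.

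Missing week-12 walks are foreseeable. After study drug is stopped, the minimum data in Protocol 5.6.2 contain no 6MWT and may be collected by telephone, and Table 6-1 has no walk at the unscheduled visit. Against that, Protocol 5.5.5 and 5.6.2 expect such patients to keep attending and to have an end-of-study visit. SAP 5 foresees Visit 6 walks taken off drug. Protocol 6 calls for an early end-of-study visit after premature study discontinuation, and SAP 6.3.5 does not say whether a walk at that visit counts as week 12.

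At stake is bias in a confirmatory contrast if patients who decline are lost unequally, with no listed analysis that would reveal it.

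**Working it through.** **1. The plan's own figure.** Inputs from SAP 4.2: difference 35 m, SD 114 m, two-sided alpha 0.05, power 90%. Normal formula: n = 2 × (1.960 + 1.282)² × 114² / 35² = 2 × 10.507 × 12,996 / 1,225 = 222.9, so 223 per group. The exact t calculation gives 224, the stated figure.

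**2. Loss of power.** With 300 per arm and a share m missing, n = 300 × (1 − m). Exact t power at 35 m, SD 114, alpha 0.05:

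| Missing | n per arm | Power |
|---|---|---|
| 0% | 300 | 96.4% |
| 10% | 270 | 94.5% |
| 20% | 240 | 91.9% |
| 25% | 225 | 90.1% |

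The required 224 are kept up to 1 − 224/300 = 25.3% missing.

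**3. Size and direction of bias, by identity.** Let m_S and m_E be the missing shares under sacubitril/valsartan and enalapril. Let L be the number of metres by which the mean change of the unobserved patients falls below that of the observed patients in the same arm. Each full-arm mean is the observed mean minus m × L. The observed difference (sacubitril/valsartan minus enalapril) is therefore off by (m_S − m_E) × L.
- Equal shares and equal L: bias 0.
- m_S = 10%, m_E = 20%, L = 50 m: −0.10 × 50 = −5 m. With L = 100 m: −10 m.
- The standard error is then 114 × √(1/270 + 1/240) = 10.1 m.

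The arm that loses more decliners looks better among those who remain.

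**4. Simulation.** The documents give no missing rate and no between-visit correlation, so all of the following is assumed: 300 per arm, SD 114 at each visit, adjacent-visit correlation 0.8, logistic dropout on decline from baseline with slope 1 (moderate) or 2 (strong) per SD of change, 18% versus 9% missing, and no true effect. NYHA was not simulated. MI was run by arm from the walks seen. Absolute bias in metres, moderate / strong:

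| What was seen before loss | Observed pairs only | After MI |
|---|---|---|
| Week 8 seen, and it drives dropout | 4.8 / 7.1 | 0.0 / 0.0 |
| Only week 4 seen; unseen week-8 decline drives dropout | 4.8 / 7.1 | 3.1 / 5.0 |
| No post-baseline walk; unseen week-4 decline drives dropout | 3.1 / 4.6 | 3.1 / 4.7 |
| Equal mix of the three | 4.2 / 6.3 | 1.7 / 2.5 |

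By the identity in step 3, a bias of 3.1 to 7.1 m at a 9-point gap corresponds to L of roughly 34 to 79 m (3.1/0.09 and 7.1/0.09).

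Other settings:
- 9% versus 4.5% missing, moderate dependence: 1.7 to 2.6 m.
- Equal 14% missing: under 0.1 m, type I error 4.5% to 5.3%.
- A true 35 m effect, one dropout rule common to both arms, 14% missing under enalapril: attenuation of 0.6 to 2.9 m.
- Dropout driven by the unseen week-12 decline itself, 18% versus 9%: 6.4 to 9.7 m, of which MI leaves 3.4 to 5.6 m.

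**The case against.** **The lists settle the reading.** SAP 6.3.5, 6.3.7 and Tables 14.2-1 to 14.2-4 agree with each other. In Protocol 9.4.2 the remark about performing both analyses alike leads straight into the hypothesis notation, and missing data has its own section, where activity is the only endpoint named. This stands. A reader might infer that the documents flatly contradict each other on 6MWT imputation. They do not: the detailed lists favour no imputation, and what remains is loose wording in Protocol 9.4.2, 9.4.3 and SAP 6.6.

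**There is partial cover.** SAP 6.6 provides an extra LOCF visit for further secondary endpoints and a worst-value rule for qualitative variables after dropout for hospitalization or death. The first may reach the secondary week-12 6MWT change and the second the 30 m responder endpoint. Neither reaches the co-primary. The blind review in SAP 6.2 leaves room for other statistical decisions before unblinding, which is where this one can be made.

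**The bias rests on assumed unequal loss.** True. Nothing in the documents supports a two-fold arm difference.

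**The type I error is easily misread.** In the 18% versus 9% runs, two-sided rejection under the null is about 7% to 14%. A reader might take that as the risk of a false win for sacubitril/valsartan. If enalapril loses more, it is the reverse: with week-8 decline driving dropout, false wins were 0.7% for sacubitril/valsartan and 7.8% for enalapril under moderate dependence, and 0.4% and 12.7% under strong. The inflation favours sacubitril/valsartan only if that arm loses more.

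**Power at the Hochberg step.** A reader might infer that power is fragile at alpha 0.025. The documents do not support a firm figure: SAP 6.4 plans no multiplicity adjustment, in conflict with SAP 4.2, and an unadjusted t-test at SD 114 understates the power of an ANCOVA that adjusts for baseline.

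**Conclusion.** The point holds as a gap in the missing-data plan for one co-primary. As listed, the 6MWT analysis uses only patients with both walks, ignores intermediate walks that are already collected, and has no sensitivity analysis that varies the missing-data assumption. That it is restricted to observed pairs follows from the written model; the SAP never says so. The label of mixed model on Table 14.2-2 does not change this, because the model in SAP 6.3.5 has one value per patient.

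None of this depends on a missing rate. The size of the bias does. It is nil under the null with equal missingness, and about 3 to 7 m of the 35 m target under the assumed 18% versus 9%. It runs in favour of the arm that loses more: against sacubitril/valsartan if enalapril loses more, and for it in the reverse case. MI removes the bias when the walk that drove dropout was observed, about a third of it when only week 4 was seen, and none without a post-baseline walk. Precision is a secondary matter, given the 25% margin. The change should be made, but the documents do not show that the co-primary result will be materially biased.

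**What to change.** Before unblinding, amend SAP 6.3.5, 6.3.7 and 6.6 and keep the stated 6MWT main population.

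- **Main method, one only:** impute week-12 distance by arm from baseline, week-4 and week-8 distance and NYHA stratum. Then fit the ANCOVA already written and pool with MIANALYZE.
- **Sensitivity analyses:** keep the ANCOVA on observed pairs. Add a delta-adjusted run over a prespecified range of deltas that is not tied to any assumed arm gap, for example 0, 35 and 70 m (none, one and two times the plan's own important difference), shifting each arm separately and both together.
- **Rules to state:** observed week-12 walks after drug stop stay in the FAS analysis (SAP 5 removes them only from PP, beyond 12 days). Say how a walk at an early end-of-study visit is used, without discarding Visit 6 walks that fall slightly outside the window in Table 6-1. Say what happens to FAS members without a baseline walk.
- **Reconcile** with Protocol 9.4.2 and 9.4.3, so that each co-primary has its missing-data method named.

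Cost: SAP wording plus choosing and programming one imputation model, since SAP 6.6 and 8.5 offer only a generic menu; one to two days is assumed. No new data are needed, as the walks at Visits 4 and 5 are already collected. The downside is that the main result then rests on missing-at-random, which the data cannot confirm and the delta run can only probe.

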6.3.6 Secondary Efficacy Analyses

Proportion of patients with improved performance (≥ 30 m) in 6-minute walking test at week 12 compared to baseline. The comparison of patient groups will be carried out using logistic regression model with factors treatment and baseline NYHA class (NYHA II vs. III/IV) and the baseline value as further covariate. The Odds Ratio for the factor treatment and its 95%-confidence interval will be given.

Proportion of patients with improved performance (≥ 30 m) in 6-minute walking test at week 12 compared to baseline in a subset of patients with baseline 6-minute walk distance equal to or less than 300 meters. The comparison of patient groups will be carried out using logistic regression model with factors treatment and baseline NYHA class (NYHA II vs. III/IV) and the baseline value as further covariate. The Odds Ratio for the factor treatment and its 95%-confidence interval will be given.

Proportion of patients with improved performance (≥ 30 m) in 6-minute walking test at week 12 compared to baseline in a subset of patients with baseline 6-minute walk distance between 100-450 meters. The comparison of patient groups will be carried out using logistic regression model with factors treatment and baseline NYHA class (NYHA II vs. III/IV) and the baseline value as further covariate. The Odds Ratio for the factor treatment and its 95%-confidence interval will be given.

Score of 6-minute walking test will be summarised at baseline, week 4, week 8 and week 12. Change from baseline values will be presented. The comparison of patient groups at week 12 compared to baseline will be analyzed using a two sample (independent group) t-test or a non-parametric Mann–Whitney–Wilcoxon (Wilcoxon rank sum) test, where applicable.

Proportion of patients who show increased levels ($\geq 10\%$ increase) of non-sedentary daytime physical activity at week 12 compared to baseline. The comparison of patient groups will be carried out using logistic regression model with factors treatment and baseline NYHA class (NYHA II vs. III/IV) and the baseline value as further covariate. The Odds Ratio for the factor treatment and its 95%-confidence interval will be given.

PGA scores will be tabulated at week 4, week 8 and week 12. The comparison of patient groups at week 4, week 8 and week 12 will be analyzed using a chi-square test or Fisher's exact test, where applicable.

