Proportion of patients with improved symptoms of HF as assessed by PGA, number and proportion will be tabulated at week 4, week 8 and week 12. The comparison of patient groups will be presented and analyzed using a chi-square test or Fisher's exact test, where applicable.

Change from baseline in mean daily non-sedentary daytime activity in weekly and two-weekly intervals will be summarised. The comparison of patient groups will be analyzed using a two sample (independent group) t-test or a non-parametric Mann–Whitney–Wilcoxon (Wilcoxon rank sum) test, where applicable.

Proportion of patients at weekly and two-weekly intervals who show increased levels ($\geq 10\%$ increase) of mean daily non-sedentary daytime physical activity compared to baseline will be tabulated. The comparison of patient groups will be presented and analyzed using a chi-square test or Fisher's exact test, where applicable.

Change from baseline in mean daily light and moderate-to-vigorous non-sedentary daytime physical activity between baseline and different time points under treatment (weekly or two-weekly from week 0 to week 12) will be summarised. The comparison of patient groups will be analyzed using a two sample (independent group) t-test or a non-parametric Mann–Whitney–Wilcoxon (Wilcoxon rank sum) test, where applicable.

Total weekly time spent in non-sedentary daytime physical activity will be summarised by week, from week 0 to week 12. The comparison of patient groups will be analyzed using a two sample (independent group) t-test or a non-parametric Mann–Whitney–Wilcoxon (Wilcoxon rank sum) test, where applicable.

[figure not shown]
Total weekly time spent in light non-sedentary daytime physical activity will be summarised by week, from week 0 to week 12. The comparison of patient groups will be analyzed using a

[figure not shown]
two sample (independent group) t-test or a non-parametric Mann–Whitney–Wilcoxon (Wilcoxon rank sum) test, where applicable.

Total weekly time spent in moderate-to-vigorous non-sedentary daytime physical activity will be summarised by week, from week 0 to week 12. The comparison of patient groups will be analyzed using a two sample (independent group) t-test or a non-parametric Mann–Whitney–Wilcoxon (Wilcoxon rank sum) test, where applicable.

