M6min (an actigraphy-based measure of the peak six minutes of daytime physical activity) will be summarised at baseline, week 2, week 4, week 6, week 8, week 10 and week 12. Change from baseline values will be presented. The comparison of patient groups at week 12 compared to baseline will be analyzed using a two sample (independent group) t-test or a non-parametric Mann–Whitney–Wilcoxon (Wilcoxon rank sum) test, where applicable.

Proportion of patients with increased M6min (an actigraphy-based measure of the peak six minutes of daytime physical activity) compared to baseline at week 4, week 8 and week 12 will be tabulated. The comparison of patient groups will be presented and analyzed using a chi-square test or Fisher's exact test, where applicable.

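### The worst-value rule after drop-out through hospitalisation or death covers week 12 only, so the earlier PGA, M6min and activity-responder tests default to observed cases, mainly at week 8 and in later activity intervals

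*SAP*

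**What the plan says.** **The rule.** SAP 6.6 opens it with "In case of qualitative (e.g., increased level of non-sedentary daytime physical activity) or semi-quantitative (e.g., PGA) efficacy variables" and then states that "missing Week 12 values of patients previously dropped out due to hospitalization or death will be substituted by the worst value possible". Its examples are 'No' for the activity responder and 'much worse' for the PGA. Protocol 9.4.3 has the same restriction: "missing Week 12 values of patients previously dropped out due to hospitalization or death".

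**The tests.** SAP 6.3.6 plans comparisons between arms before week 12 for variables of this kind:

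- PGA score: "The comparison of patient groups at week 4, week 8 and week 12 will be analyzed using a chi-square test or Fisher's exact test".
- PGA improvement: "number and proportion will be tabulated at week 4, week 8 and week 12", with a chi-square or Fisher test.
- Increased M6min: "compared to baseline at week 4, week 8 and week 12 will be tabulated", with a chi-square or Fisher test.
- The ≥10% activity responder: a chi-square or Fisher test at weekly and two-weekly intervals.

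M6min is not named in the rule. Its responder endpoint is a yes/no variable and so falls under the word qualitative, as the activity responder does.

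**The concern.** The sponsor has decided that, for these variables, leaving through hospitalisation or death is a bad outcome and not an uninformative gap. The decision is applied at one time point, while the same variables are tested at several. The documents give no reason why a death should count at week 12 and not at week 8.

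Two things are at stake. First, the earlier tests compare patients who did not leave for the worst reasons, so an arm that loses more such patients is not penalised there. Second, the time course is itself of interest: protocol Table 2-1 says the weekly intervals serve to analyse the dynamics of change. If only the last point includes the patients lost, part of any fall in responders at week 12 comes from the rule and not from the patients.

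**Working it through.** The plan states no figure that depends on this rule, so there is none to reproduce. The check is textual, followed by an illustration of size.

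**Step 1: does any other rule reach weeks 4 and 8?**

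| Rule | Where | Reach |
|---|---|---|
| Multiple imputation | SAP 6.6, protocol 9.4.3 | Missing baseline, activity in weeks 10–12, and a key secondary variable |
| LOCF | SAP 6.6 | Activity in weeks 10–12 and the key secondary variable; for further secondary endpoints, an extra end-of-study visit beside week 12 |
| Worst value | SAP 6.6, protocol 9.4.3 | Week 12 |

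None supplies a missing week 4 or week 8 PGA or M6min value, or a missing responder value in an earlier activity interval. Without a rule, a chi-square or Fisher test uses the values available.

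**Step 2: who is affected?** SAP Appendix 8.1 places these tables in the FAS. SAP 5 requires, for at least one primary endpoint, a baseline and a post-baseline value. In protocol Table 6-1 the first scheduled post-baseline 6MWT and the first scheduled post-baseline actigraphy download are both at Visit 4 (week 4).

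- Lost before week 4: usually outside the FAS at every time point, unless an early end-of-study or unscheduled visit gave a primary value.
- Attended week 4, died in week 6: in the FAS, observed at week 4, absent at week 8, and 'much worse' or 'No' at week 12.

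The gap therefore lies mainly at week 8 and in the later activity intervals.

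**Step 3: size.** From the documents: 300 per arm (SAP 4.2). Assumed, because the documents give neither: the share *d* lost through hospitalisation or death before the visit, and the proportion *p* improved among those observed.

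- Observed-case difference: pA − pB
- Worst-value difference: pA(1 − dA) − pB(1 − dB)
- Shift: pB·dB − pA·dA, which is p(dB − dA) when both arms have the same p
- Standard error of the difference: √(2p(1 − p)/300)

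With the same p in both arms:

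| Lost, A v B | Patients lost | p = 40% | p = 60% |
|---|---|---|---|
| 1% v 3% | 3 v 9 | 0.40 × 0.02 = 0.8 points | 0.60 × 0.02 = 1.2 points |
| 1% v 5% | 3 v 15 | 0.40 × 0.04 = 1.6 points | 0.60 × 0.04 = 2.4 points |

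Standard error: √(2 × 0.4 × 0.6/300) = 4.0 points at 40% or 60%, and √(2 × 0.5 × 0.5/300) = 4.1 points at 50%.

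Other cases:

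- 2% lost in each arm, 50% improved in both: the difference does not change, but each proportion falls from 50% to 0.50 × 0.98 = 49%.
- 2% lost in each arm, 55% v 45% improved: 0.539 − 0.441 = 9.8 points instead of 10.0, a shift of −0.2 points.
- 4% v 2% lost, 55% v 45% improved: 0.45 × 0.02 − 0.55 × 0.04 = −1.3 points.
- 3% v 6% lost, 50% improved in both: 0.50 × 0.03 = +1.5 points.

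The sign depends on which arm loses more patients. The arithmetic covers the yes/no variables; the seven-category PGA score test was not sized.

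**The case against.** The strongest reply is that the plan is consistent in its own way: multiple imputation, LOCF and worst value all serve the end of study, and interim visits get no imputation under any method. Observed-case summaries at interim visits are a common choice for exploratory endpoints. The earlier proportions are too high only if worst value is also the intended target at those visits, which the documents do not say. This stands in part: the plan may intend observed cases, but it does not say so, and the same variable is then handled in two ways within one time course.

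A second reply is that the gap would be visible. SAP 6.3.2 reports numbers of missing values, and deaths, discontinuations and individual PGA data are listed. That is true, but the planned tests would still run on the reduced denominators.

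A reader might infer more than the documents support:

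- **That the SAP plans to exclude these patients.** It does not say this. Observed-case handling follows from the absence of a rule.
- **That week 4 is affected as much as week 8.** Most patients lost before week 4 are missing because of the FAS definition, at week 12 as well, and extending the rule would not bring back those outside the FAS.
- **That equal losses always leave the difference unbiased.** They do so only if responder rates are equal.
- **That the gap favours one treatment.** Nothing in the documents fixes the direction.

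**Conclusion.** The point holds as a minor inconsistency. Followed as written, the plan counts the same event as the worst outcome at week 12 and as a missing value before it, for variables tested at both times. Under the assumed losses the shift is about 1 to 2 percentage points, roughly a quarter to 0.6 of a standard error, and the 1% v 5% case has no support in the documents beyond being an assumption. All sizes rest on assumed drop-out and responder rates and on 300 analysed per arm; the FAS would be somewhat smaller.

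Neither primary endpoint is touched. Protocol 9.5.1 makes all secondary tests exploratory, so no confirmatory conclusion depends on this. It is worth correcting because the change is cheap and makes the time points comparable.

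**What to change.** In SAP 6.6, replace the reference to missing week 12 values with missing values at every scheduled visit or interval after the drop-out, for the same qualitative and semi-quantitative variables. Name the M6min responder among the examples. Because protocol 9.4.3 carries the same week 12 limit, record the departure in SAP 6.1 or amend 9.4.3; editing the SAP phrase alone would leave the two documents in conflict. Do this before the blind is broken.

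If the sponsor prefers observed cases before week 12, the minimum is to say so and to report missing counts by reason and arm at each visit and interval.

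The cost is minor programming, the declared change, and slightly less favourable interim proportions. Patients outside the FAS are not recovered by either option.
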